Specific Aim 1: To investigate that increased DA transmission normalizes reward responsiveness and optimism in females with histories of CSA. We will use reward paradigms from our pilot work in conjunction with a pharmacological challenge to test that decreased phasic DA transmission within mesolimbic regions plays a key role in CSA sequelae. We hypothesize that increased phasic DA release – achieved through presynaptic DA autoreceptor blocking by means of single low dose of the D₂/D₃ antagonist amisulpride – will improve positive reinforcement learning and boost activation in reward-related brain regions, particularly the ventral and dorsal striatum (**Hypothesis 1a**). Due to hypothesized downregulation of mesolimbic DA pathways, we expect that individuals with CSA and current MDD (“CSA/MDD”) will show the largest improvements. Confirming that a well-functioning reward system is a marker of resilience, adults with CSA without lifetime psychopathology (“CSA/RES”) will show normative activation and performance under placebo (**Hypothesis 1b**). We also hypothesize that increased phasic DA release – achieved through amisulpride – will re-orient MDD individuals from a pessimistic outlook to an optimistic outlook as measured by the Optimism Bias Task (**Hypothesis 1c**). In addition, under placebo, MDD participants will show a pessimistic outlook as compared with healthy controls (**Hypothesis 1d**).

Specific Aim 2: To investigate dopamine transporter and its relation to reward processing in females with CSA history. We will utilize positron emission tomography (PET) and a highly selective radioactive ligand (¹¹C-altropane) to assess DAT binding in CSA adults. Animal studies have shown that early adversity leads to DAT downregulation within mesolimbic regions. In humans, we have observed links between altropane binding and depressive symptoms, the most common CSA sequelae). Based on our data, we expect that, relative to control and CSA/RES subjects, CSA/MDD adults will show reduced altropane binding (**Hypothesis 2a**). We further hypothesize that, among the CSA/MDD group, reduced DAT will correlate with blunted reinforcement learning and striatal activation (**Hypothesis 2b**).

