
concentrations of electrolytes, BUN, SGOT, SGPT, CPK, alkaline phosphatase, total bilirubin, albumin, total protein, blood pregnancy test, TSH, eGFR, and electrocardiogram (EKG), and a urine drug test. These tests must be performed within four weeks prior to amisulpride administration.

Preliminary screening for sex, handedness, neurological disorders, exclusionary physical conditions, medication status, weight, history of childhood trauma and history of depression, and MRI and PET safety will take place at the time of the initial telephone contact or interview or via the online screening survey on RedCap (a Partners secure website). Subjects will be re-screened for MRI safety at the beginning of the fMRI session.

To avoid the confounding effects of medication, only subjects off medication will be considered. Importantly, no subject will be requested to discontinue treatment for the purpose of participating in the studies proposed here. Further, if any subject becomes emergently ill or suicidal, access to emergency clinical care will be provided according to established procedures at McLean Hospital. If at any point between signing of consent and the conclusion of the second session, a subject becomes suicidal, homicidal, manic, or psychotic, (s)he will be withdrawn from the study and appropriate care and resources will be provided. Depending on the outcome of the first session, eligible participants will be assigned to one of four groups: (1) CSA between the ages of 5-14 with current diagnosis of MDD (*CSA/MDD*), (2) CSA between the ages of 5-14 without current or past diagnosis of Axis I or II disorders (*CSA/RES*), (3) current diagnosis of MDD without a history of CSA (*MDD*), and (4) healthy controls. Each group will contain 23 subjects who complete at least two imaging sessions (n=23/group).

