A *Group* (CSA/MDD, CSA/RES, MDD, controls) x *Drug* (amisulpride, placebo) x *Trial Type* (PSST: Choose A, Avoid B or MID: Reward, loss, no-incentive) ANOVA will be run. Based on prior findings, we expect a significant *Drug x Trial Type* interaction, due to larger positive reinforcement learning but lower negative reinforcement learning in the amisulpride relative to the placebo group. Moreover, although amisulpride is expected to affect reinforcement learning in all groups, we hypothesize that CSA/MDD subjects will show the largest gains, leading to a significant *Group x Drug x Trial Type* interaction. Planned contrast will show no difference in positive reinforcement learning between controls receiving placebo and CSA/MDD subjects receiving amisulpride. To test Hypothesis 1b, a *Group x Drug x Trial* ANOVA is expected to yield no group differences between CSA/RES and controls and significant differences to the CSA/MDD in the placebo condition and CSA/MDD subjects receiving amisulpride.

fMRI Analyses

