Analyses will be conducted using FreeSurfer (Fischl et al 2002, 2004). Volumetric analysis will be conducted and, if applicable, fMRI data will be adjusted for volumetric group differences. Pre-processing will include motion/slice-time correction, removal of slow linear trends, intensity normalization, and spatial smoothing (6-mm). The hemodynamic response will be modeled as a gamma function (2.5 s delay to rise, 1.25 s dispersion time) and convolved with stimulus onsets. Data will be analyzed using two approaches: an ROI approach to evaluate *a priori* hypotheses and a whole-brain approach to test finding specificity. In the first, regression coefficients (“beta weights”) will be extracted from ROIs obtained from FreeSurfer’s parcellation and selected based on prior studies (Knutson & Cooper 2005). ROIs will include basal ganglia regions (globus pallidus, NAc, caudate, putamen), dorsal/ rostral anterior cingulate, vmPFC, and OFC. For each subject and ROI, beta weights will be entered into *Group* x *Condition* (amisulpride, placebo) x *Hemisphere* x *Trial* (reward, loss, no-incentive) ANOVAs. We expect that the main effects of *Group* (controls \approx CSA/RES > MDD > CSA/MDD) and *Condition* (amisulpride > placebo) will be significant. Moreover, although amisulpride will increase basal ganglia responses to reward – but not punishment or no-incentive – cues in all groups, we expect that the CSA/MDD group will show the greatest improvements (significant *Group* x *Condition* x *Cue* interaction). Planned contrast will show no difference between controls and CSA/RES receiving placebo, and CSA/MDD subjects receiving amisulpride will show similar activation as controls under placebo. In the second approach, whole-brain analyses will be run. Each subject’s data will first be re-sampled into Talairach space and random effects analyses will be run. Significance levels in the fMRI data will be set to yield a corrected mapwise significance level of $p < .05$.

PET Analyses

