Comparison of Molecular and Cellular Properties of Converted DA Neurons from Fibroblasts of MDD/CSA (n=8), CSA/RES (n=4), and Psychiatrically Healthy Subjects (n=8): Once we optimize conversion of fibroblasts to mDA neurons, we will use these biopsied fibroblasts to convert them to mDA neurons using our optimized protocol. To evaluate whether converted DA neurons from each group have distinct properties, we will test their ability to synthesize and release DA in response to membrane depolarization. We will treat *in vitro* differentiated cells with 50 mM KCl for 30 minutes and assess DA release by HPLC. Media will be collected after 30 min then concentrated perchloric acid (PCA) will be added to a final concentration of 0.1 M PCA/0.1mM EDTA. The DA content of the supernatants will be measured by reverse-phase HPLC. We will also compare mRNA expression patterns for dopamine-related genes such as synthesizing (TH and AADC), uptake (DAT), degrading (MAO and COMT), and storage function (VMAT2) at mRNA and protein levels in converted mDA neurons of each group.

Plasma Samples

Concentrations of pro- and anti-inflammatory cytokines and related receptors will be assessed using enzyme-linked immunosorbent assays (ELISA, R&D systems, Minneapolis, MN). All assays will be performed at the CLIA-certified Harvard Catalyst Central Laboratory (HCCL) in accordance with manufacturer specifications, and will be run in duplicate.

b. Study endpoints

Not applicable

c. Statistical methods

Please see above.

d. Power analysis

Sample size and power calculations

Sample size was estimated after considering effect sizes obtained in preliminary studies. Effect sizes were calculated using $p = 0.05$ for detecting differences between (1) controls vs. CSA/MDD, and (2) CSA/MDD receiving a DA challenge vs. placebo. Based on these estimates and allowing for 5% data loss, the sample size is 92 (23 subjects/group). In our study using the PSST task proposed, relative to controls, women with histories of CSA and MDD showed lower accuracy in trials in which they needed to rely on reward (Cohen's $d = -0.85$). In a study using the probabilistic reward task, we found that unmedicated MDD subjects had significantly reduced response bias compared to controls ($d = -0.70$; [name] et al 2009b). In another study using the same task, we found that healthy subjects receiving

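### Return to control level under amisulpride, and normality of CSA/RES under placebo, are tested only by contrasts predicted to show no difference, in cells of 11-12 and with no margin or interval criterion

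*Combined protocol and SAP*

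**What the plan says.** Specific Aim 1 proposes that raising dopamine transmission normalises reward responsiveness. Hypothesis 1b adds that the CSA/RES group "will show normative activation and performance under placebo".

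The matching analyses are in section VI.a.

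- **Behaviour, return to control level** (Amisulpride Behavioral Analyses for PSST and MID): "Planned contrast will show no difference in positive reinforcement learning between controls receiving placebo and CSA/MDD subjects receiving amisulpride".
- **Behaviour, resilience** (same subsection): the ANOVA for Hypothesis 1b "is expected to yield no group differences between CSA/RES and controls". The sentence goes on to expect "significant differences to the CSA/MDD in the placebo condition and CSA/MDD subjects receiving amisulpride".
- **fMRI, resilience** (fMRI Analyses): "Planned contrast will show no difference between controls and CSA/RES receiving placebo".
- **fMRI, return to control level** (same sentence): "CSA/MDD subjects receiving amisulpride will show similar activation as controls under placebo".

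The same subsections also predict a Drug x Trial Type interaction, a three-way interaction with the largest gain in CSA/MDD, and main effects of group and drug condition on fMRI.

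On numbers, section VI.d states: "allowing for 5% data loss, the sample size is 92 (23 subjects/group". Section IV.a states: "Each group will contain 23 subjects who complete at least two imaging sessions (n=23/group". The Randomization text in section V.a gives half of each group placebo and half amisulpride. Section VI.d gives power only for detecting differences. Sections VI.b and VI.c add no endpoint or method. No equivalence margin, equivalence test or interval rule appears in the document.

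**The concern.** A contrast that is meant to come out null is more easily confirmed when the data are scarce or noisy. With no margin or interval criterion, the only result the plan offers in support of return to control level, or of CSA/RES normality, is a non-significant comparison of two half-groups. A deficit of the size the trial targets could remain and still give that result. Both conclusions are central to Aim 1.

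The Hypothesis 1b sentence adds a drafting problem. Its last clause can be read as predicting that amisulpride-treated CSA/MDD subjects differ significantly from the comparison groups. The sentence before it and the fMRI subsection predict that they do not differ from controls on placebo.

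**Working it through.** **Inputs.** From section VI.d: 92 subjects, 23 per group, p = 0.05 (sidedness not stated), PSST deficit in women with CSA and MDD |d| = 0.85, mean behavioural |d| = 1.00, mean fMRI |d| = 1.15. From section V.a: 50:50 drug split within group.

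**1. The plan's own power figure.** For n per group, one-sided 0.05, normal approximation: power = Φ(d√(n/2) − 1.645). With n = 23, √11.5 = 3.391.

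- d = 1.00: Φ(3.391 − 1.645) = Φ(1.746) = 0.960.
- d = 1.15: Φ(3.900 − 1.645) = Φ(2.255) = 0.988.

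The stated bound of more than 0.95 reproduces for whole groups, 23 v 23, one-sided. Two-sided it would be 0.924 at d = 1.00 and 0.974 at d = 1.15. It does not describe the half-group contrasts.

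**2. Cell size.** 92/4 = 23 per group and 23/2 = 11.5, so 11 or 12 per group-by-drug cell. If 5% is lost from 23, 23 × 0.95 = 21.85, or about 11 per cell.

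**3. Chance of a non-significant contrast when a difference exists.** Two-sided 0.05, 11 v 12. Standard error in SD units = √(1/11 + 1/12) = 0.417. Non-centrality = d/0.417. Two versions are shown: a stand-alone t-test (21 df, critical value 2.080) and a contrast using pooled ANOVA error (92 − 8 = 84 df, critical value 1.989, equal variances assumed).

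| True d | Meaning | Non-significant, 21 df | Non-significant, 84 df |
|---|---|---|---|
| 0.425 | half the PSST deficit remains | 84% | 83% |
| 0.85 | PSST deficit fully uncorrected | 51% | 48% |
| 1.00 | plan's mean behavioural effect | 37% | 34% |
| 1.15 | plan's mean fMRI effect | 25% | 22% |

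**4. Precision.** 95% interval half-width: 2.080 × 0.417 = 0.87 SD (21 df), or 1.989 × 0.417 = 0.83 SD (84 df). An observed difference of zero would therefore be compatible with a deficit about as large as the cited one.

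**5. Would a formal equivalence test work?** The documents give no margin, so these are assumptions. If two cells of 11 and 12 are truly identical, two one-sided 0.05 tests conclude equivalence about 19% of the time at a 0.8 SD margin and about 0.1% at 0.5 SD. For 80% power the normal formula, 2[(1.645 + 1.282)/margin]², gives 27 per cell at 0.8 SD and 69 at 0.5 SD.

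**6. How often would a 95% interval exclude a given deficit if the cells are truly equal?** This mirrors step 3: 49-52% for a deficit of 0.85 SD, and 16-17% for 0.425 SD.

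**The case against.** **The no-difference contrasts are not the whole case.** A reader might infer from the 48-51% that an ineffective drug would be declared normalising about half the time. The documents do not support that, because the plan predicts a wider pattern. I simulated a 0.85 SD deficit that the drug leaves untouched (12 controls on placebo, 12 CSA/MDD on placebo, 11 CSA/MDD on amisulpride, 84 error df). No difference, a significant placebo deficit and a significant drug gain within CSA/MDD occur together only about 2% of the time. The within-CSA/MDD gain stands in for the interaction. For resilience, if CSA/RES truly shares the deficit, no difference from controls together with a significant difference from CSA/MDD is also about 2%.

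This objection stands against the strong reading, but it has limits. The plan does not say that all elements must hold together. If half the deficit is corrected, the full pattern still appears about 14% of the time and the null contrast alone about 83%. None of the other predicted effects tests return to control level or CSA/RES normality.

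**The plan never says that non-significance will be treated as equivalence.** That is correct. The text states predictions, not a decision rule, so such a reading is an inference. What can be said is that no other criterion is supplied.

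**The Hypothesis 1b sentence might be taken as an opposite prediction for the same contrast.** That is only one reading of a badly built sentence. Its last clause may mean CSA/MDD on placebo against CSA/MDD on amisulpride, or may place the treated CSA/MDD subjects in the no-difference set. The neighbouring text states one direction clearly. This is an ambiguity to reconcile, not a demonstrated contradiction of intent.

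**Section III.b mentions 184 subjects.** The sample-size text uses 92, with 23 completers per group. Cells of 23 would need all 184 to be analysed, which the plan does not say.

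**Conclusion.** The point holds as a gap in the analysis text. Return to control level and CSA/RES normality are tested only by contrasts predicted to be null, between cells of about 11-12, with no margin or interval criterion. A full PSST-sized difference would be missed about 48-51% of the time and a half-sized one about 83-84%. The 95% interval half-width is 0.83-0.87 SD.

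These figures assume 92 analysed subjects, an even split by drug, two-sided 0.05, normal data and equal variances. Completing two imaging sessions does not by itself guarantee usable fMRI or PSST data, so 11-12 is closer to a ceiling than a floor.

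The finding does not extend to the tests of drug gain or of the placebo deficit. Nor does it show that the plan's full predicted pattern would often appear by chance.

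**What to change.** In both VI.a subsections (behavioural and fMRI):

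1. Report each of these contrasts as an estimate with a 95% confidence interval, or a 90% interval if an equivalence margin is pre-stated.
2. State that a non-significant contrast alone will not be called normalisation or resilience. Either claim requires the interval to exclude a pre-stated deficit; otherwise the result is inconclusive.
3. Justify that deficit from outside the trial data and date it. The Randomization text says the blind was broken in May 2016 for preliminary analyses, so the choice should visibly not depend on them. A threshold equal to the whole 0.85 SD is lenient: excluding it shows only that the full deficit does not remain.
4. Rewrite the Hypothesis 1b sentence so that the comparison with amisulpride-treated CSA/MDD subjects has one predicted direction, consistent with the sentence before it and with the fMRI subsection.

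A formal equivalence test need not lead, since its power here is about 19% at an assumed 0.8 SD margin and near zero at 0.5 SD.

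The change is to wording and reporting, with no new subjects or procedures. The cost is in the conclusions. Even if the cells are truly equal, the 95% interval would exclude 0.85 SD only about half the time and 0.425 SD about one time in six, so most no-difference claims will read as inconclusive.

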Subjects will be paid \$15/hour for the SCID session (session 1), up to \$70 for the ERP session including \$38 for completing the EEG and up to \$32 on the probabilistic reward task, up to \$150 for the fMRI session including \$100 for completing the session and up to \$50 on the MID task, and \$200 for the PET session. In addition, participants who complete all four sessions of the study will earn an additional \$75. Lastly, if participants complete only part of a study session, they will be compensated in a prorated manner, such that if they complete half of a study session, they will be compensated half of the total amount (e.g., participant completes half of the PET scan session, he/she will be compensated \$100). If the participant completes all of the sessions, they can earn up to \$555. The subset of subjects who participate in the additional skin fibroblast study (n=20) will be compensated \$100.

Randomization

For protocol 2010-P-002593, all subjects in study are administered a single low dose of amisulpride (50 mg) in order to test the role of dopaminergic mechanisms in the pathophysiology of MDD. This proof-of-mechanism study uses a double-blind, placebo-controlled between-subject design (for each group in study, 50% of the subjects in each group will receive placebo, with the remaining 50% receiving a single dose of amisulpride), involves a single MRI session, and does not include a treatment component. Though data collection has not yet been completed, the blind was broken as of May 2016 to conduct preliminary analyses. Accordingly, the medication blind will be broken as of November, 2016 in order to allow further analyses. In order to preserve the scientific integrity of the study, we propose the following precaution:

The Research Assistant responsible for running participants ([name]), the study doctors ([name], [name]), and any other member of the [name] Lab who directly interacts with participants will remain blind to drug group assignment. Accordingly, if we discover during statistical analyses that a few participants yielded unusable data (e.g., due to excessive motion artifacts), we will be able to enroll and test a few final participants in a fully unbiased way.

b. Drugs to be used

Amisulpride

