a single dose of pramipexole – hypothesized to reduce phasic DA transmission due to inhibition of presynaptic autoreceptors – had significantly lower reward learning than those receiving placebo ($d = -1.45$; [name] et al 2008b). In an fMRI study using the MID task, relative to controls, a maltreated sample showed weaker activation to reward-predicting cues in the left putamen ($d = -0.54$) and left pallidus ($d = -1.02$), yielding a mean effect size of -0.78 . In a separate study using the MID task, unmedicated MDD subjects showed weaker activation than controls in response to gains in the caudate ($d = -0.98$), left NAc ($d = -0.73$) and left putamen ($d = -0.78$) during reward anticipation ([name] et al 2009a), yielding a mean effect size of -0.87 . In a pharmacological fMRI study in unmedicated MDD subjects we found that a single 150 mg dose of Bupropion – assumed to partially block DAT – increased reward-related responses in components of the brain’s reward circuit, including the midbrain ($d = -1.88$), subcallosal gyrus ($d = -1.64$), and SLEA ($d = -1.89$), leading to an mean effect size of -1.80 ([name] et al 2008a). In sum, based on the effect sizes we have observed for the behavioral (mean $d = -1.00$) and fMRI (mean $d = -1.15$) components, a total of 92 subjects leads to a power >0.95 of detecting group differences.

For the PET study, secondary analyses of altropane data collected in ADHD and control samples (Spencer et al 2007) indicated that a history of depression and/or current subthreshold depressive symptoms were linked to decreased DAT binding ($d = -0.58$). Because this sample was carefully screened to exclude current, clinically significant depressive symptoms and because analyses did not involve the recently developed Bayesian method, we expect that effect size between control and CSA/MDD groups will be larger (expected $d > 0.80$). Thus, 92 subjects leads to a power >0.85 of detecting group differences.

VII. RISKS AND DISCOMFORTS

a. Complications of surgical and non-surgical procedures

Maastricht Acute Stress Test (MAST)

The risks associated with the stress manipulation are minimal. This manipulation has been implemented in numerous labs due to its efficiency and safety. First of all, it is a non-intrusive manipulation that causes only very minor pain, if any. Secondly, at all times participants are allowed to remove their hand from the cold water and thus immediately stop the manipulation.

EEG

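### The fMRI plan predicts a drug effect on reward cues only, but the one overall drug test it names averages over all three trial types

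*Combined protocol and SAP*

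**What the plan says.** Section VI.a, fMRI Analyses, takes beta weights from each region of interest into a Group x Condition x Hemisphere x Trial ANOVA. Condition is amisulpride or placebo, and Trial has three levels (reward, loss, no-incentive). The regions are the basal ganglia plus cingulate, ventromedial prefrontal and orbitofrontal cortex. Three kinds of result are predicted:

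- main effects of Group and of Condition;
- a Group x Condition x Cue interaction, with the largest gain in CSA/MDD (Cue is evidently the Trial factor);
- planned contrasts between cells: controls v CSA/RES, both on placebo, and CSA/MDD on amisulpride v controls on placebo. No cue type is given for these.

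The Condition prediction runs straight into a statement about cue type: "amisulpride > placebo) will be significant. Moreover, although amisulpride will increase basal ganglia responses to reward – but not punishment or no-incentive – cues". The plan says that this holds in every group.

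Hypothesis 1a (section II, Specific Aim 1) is broader. It says that amisulpride will "boost activation in reward-related brain regions, particularly the ventral and dorsal striatum", with no cue type.

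For behaviour (section VI.a, Amisulpride Behavioral Analyses for PSST and MID), the plan does name the two-way Drug x Trial Type interaction. It expects it "due to larger positive reinforcement learning but lower negative reinforcement learning in the amisulpride relative to the placebo group", and adds the three-way term with Group.

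**The concern.** A drug effect that is present for one of three trial types, in all groups, is a Condition x Trial effect. The Condition main effect averages it with two trial types for which the plan predicts nothing. This has two consequences.

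- **Lost power.** A true reward-only effect is diluted, so a non-significant main effect could be read as evidence against a prediction that is correct.
- **Lost specificity.** A drug-related shift of the same size in all trial types would make the main effect significant, although the plan predicts no change for two of them. A significant result could then be read as support for a reward-specific mechanism.

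The term that separates the two patterns is named for behaviour and omitted for imaging.

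**Working it through.** **Inputs from the documents** (section VI.d unless stated)

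- Alpha: "Effect sizes were calculated using $p = 0.05$ for detecting differences between" the comparison groups. Sidedness is not stated; two-sided is used here.
- Sample size: "allowing for 5% data loss, the sample size is 92 (23 subjects/group".
- Allocation (Randomization section): "50% of the subjects in each group will receive placebo, with the remaining 50% receiving a single dose of amisulpride". This gives about 46 v 46 overall and 12 v 11 within a group.
- Effect sizes: a mean fMRI d of 1.15 in absolute value, and for the cited single-dose bupropion fMRI study "leading to an mean effect size of -1.80".

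**Assumptions not in the documents:** equal SDs for the three trial types (betas averaged over hemispheres), correlation r between trial types of 0.3 to 0.7, and all 92 subjects with usable fMRI data. The 0.5 and 0.8 SD effects are illustrative.

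**Step 1. The plan's own figure.** The plan states "fMRI (mean $d = -1.15$) components, a total of 92 subjects leads to a power >0.95 of detecting group differences". The mean is (0.78 + 0.87 + 1.80)/3 = 1.15. At 23 v 23 the noncentral t gives power 0.968, and at 22 v 22 (after 5% loss) 0.961. The stated figure reproduces, for a two-group comparison of a single response measure.

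**Step 2. Formulas for a reward-only effect of d SD.**

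- Mean of three trial types: raw effect d/3, SD = sqrt((1 + 2r)/3). Standardised effect = (d/3)/sqrt((1 + 2r)/3) = d/sqrt(3(1 + 2r)).
- Reward minus the mean of the other two: raw effect d, SD = sqrt(1.5(1 - r)). Standardised effect = d/sqrt(1.5(1 - r)).

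The divisor for the main effect is sqrt(4.8) = 2.19 at r = 0.3, sqrt(6) = 2.45 at r = 0.5 and sqrt(7.2) = 2.68 at r = 0.7.

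**Step 3. Power at 46 v 46** (two-sided 0.05, noncentral t, 84 error df)

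| Reward-only effect | Test | r = 0.3 | r = 0.5 | r = 0.7 |
|---|---|---|---|---|
| 0.80 | Condition main effect | 0.41 | 0.34 | 0.29 |
| 0.80 | Reward minus others | 0.96 | 0.99 | 1.00 |
| 1.15 | Condition main effect | 0.70 | 0.61 | 0.53 |
| 1.15 | Reward minus others | 1.00 | 1.00 | 1.00 |
| 1.80 | Condition main effect | 0.97 | 0.94 | 0.89 |
| 1.80 | Reward minus others | 1.00 | 1.00 | 1.00 |

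Worked example, d = 1.15 and r = 0.5: the main effect is 1.15/2.449 = 0.469, power 0.61; the contrast is 1.15/sqrt(0.75) = 1.328, power about 1.00. The gap narrows at lower correlation: at r = 0 and d = 0.80 the powers are 0.59 and 0.87.

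**Step 4. A non-specific shift.** A shift of 0.5 SD in all three trial types has standardised main effect 0.5/sqrt((1 + 2r)/3) = 0.685, 0.612 and 0.559 at r = 0.3, 0.5 and 0.7. The main effect is then significant with probability 0.90, 0.83 and 0.76. A uniform shift of 1.15/3 = 0.38 SD gives exactly the main-effect power of a reward-only 1.15 SD effect, so that test cannot tell the two apart. In simulation (4 x 2 x 3 mixed ANOVA, 23 per group split 12 v 11, 4,000 runs) the Condition x Trial test rejects at about 0.05 under the uniform 0.38 SD shift.

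**Step 5. Does the named three-way term fill the gap?** In the same simulation:

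- Reward-only effect equal in all groups: the three-way term rejects at about 0.05.
- 1.15 SD in CSA/MDD and 0.575 SD elsewhere: power is 0.11 to 0.21 for the three-way term, 0.25 to 0.35 for the Condition main effect, and 0.86 to 1.00 for Condition x Trial (2-df F test).

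**The case against.** The strongest reply is that only a label is missing. Trial is in the model, the sentence about reward cues states the two-way prediction in words, and the same ANOVA will print that term. Nor is the plan self-contradictory, since a reward-only increase implies a non-zero Condition main effect. All of that is true. But the plan does state which terms it expects to be significant, and for fMRI the two-way term is not among them.

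Three stronger readings are tempting and should not be drawn.

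- **That the main effects are the only fMRI evidence named.** They are not: the three-way interaction and the cell contrasts are named too. They answer other questions. Nor is any test labelled as the test of Hypothesis 1a. The link is an inference from the hypothesis wording, which itself sets no cue restriction; that restriction appears only in the analysis section and only for basal ganglia responses.
- **That the effect is diluted threefold.** This is exact for the raw mean. On the standardised scale, which governs power, it would need a correlation of 1.
- **That the Group main effect is diluted in the same way.** The reward-only statement concerns the drug. The predicted ordering of groups is not limited to reward cues, so the text does not support this.

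The size of the loss also depends on the effect. If the true drug effect were as large as in the bupropion study, the main effect would be adequately powered. The specificity problem would remain.

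**Conclusion.** The concern holds for the drug prediction. For an effect in all groups confined to reward cues, the fMRI section names an averaged main effect and leaves out the interaction that expresses the prediction. The standardised effect falls by a factor of 2.2 to 2.7. The power loss is serious at 0.8 SD, material at the plan's own 1.15 SD and modest at 1.80 SD. At every effect size the main effect cannot distinguish a reward-specific response from a general one.

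The figures rest on the assumed correlation, equal variances and 92 usable scans. The plan's 23 per group are subjects who complete at least two imaging sessions, so fMRI numbers could be lower. The 1.15 is a blend of group and drug effects, used here only because it is the plan's own planning value. The mismatch between prediction and named test does not depend on any of these. It is worth correcting, but it does not make the planned model unusable.

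**What to change.** In section VI.a, fMRI Analyses:

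1. Name the Condition x Trial contrast (reward minus the mean of loss and no-incentive) in the basal ganglia regions as the test of the drug prediction under Hypothesis 1a.
2. Keep the Condition main effect as a check for non-specific change.
3. State that the planned contrasts involving placebo cells use reward-cue responses.

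The cost is a few sentences. The same model is fitted to the same data, and the wording would match the behavioural section. The one downside is that a significant Condition main effect would no longer count on its own as support for the reward-specific prediction.
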